8.3.1.	Reporting Timelines.....	37
8.3.2.	Subject Follow up	37
8.3.3.	Blinding.....	37
9.	Reference	38

Study Synopsis

STUDY TITLE	PROOF: Evaluating the Performance of the KODEX-EPD CRyO balloon Occlusion Feature in patients with atrial fibrillation
STUDY PHASE	Post-market
INVESTIGATIONAL PRODUCT	KODEX-EPD System, KODEX-EPD data collection accessories
INDICATION	Patients with Atrial Fibrillation
OBJECTIVE	Performance of KODEX-EPD PV occlusion feature as compared to conventional venographic method of fluoroscopy with contrast dye in cryoballoon procedures that is used to guide the procedure. Performance will be calculated in terms of accuracy, sensitivity, specificity and positive and negative predictive values. In the blinded arm of the study, the operator will be blinded for the PV occlusion data on the KODEX-EPD system and this data will not be used for clinical guidance.
STUDY DESIGN	Prospective, multi-center, non-randomized, open label, double arm study
# OF SUBJECTS	The study will include a maximum of 20 patients per center at 2 centers in the blinded to KODEX arm of the study. An additional 25 patients will be included at UZ Brussel in the KODEX guided arm of the study.
STUDY DURATION	18 months
STUDY POPULATION	Arrhythmia patients scheduled to undergo a cryo balloon ablation procedure for their atrial fibrillation. Both male and female subjects who meet all eligibility criteria and give written informed consent will be enrolled in the study. Inclusion criteria: 1. Subject must be aged >18 years. 2. Subject must have signed a written Informed Consent form to participate in the study, prior to any study related procedures.

	
3. Subject must be willing to comply with the protocol requirements.
 
4. Subject receives a de novo ablation procedure for treatment of atrial fibrillation.
 
Exclusion criteria; Pregnant women.


STUDY VISIT SCHEDULE AND PROCEDURES
	
This is an acute study with no follow-up.
 
Before the procedure (Baseline):
 
 1. Eligibility according to inclusion and exclusion criteria 2. Obtaining signed Informed Consent Form (ICF) 3. Demographics 4. Medical history 5. Physical examinations 6. Concomitant medications 7. Presence/history of atrial fibrillation 8. Previous and current treatments of atrial fibrillation 
During procedure:
 
 1. Delivery of standard therapy. The study device will be used in the cryoballoon ablation procedure according to the instructions for use. PV occlusion will be assessed with the KODEX-EPD PV occlusion feature. 
 - Blinded Arm; The physician will be blinded for the KODEX-EPD occlusion data and use conventional venographic method of fluoroscopy with contrast dye to guide the procedure. - KODEX guided Arm; the physician will use the KODEX-EPD occlusion data to guide the procedure 2. Confirmation of therapy. Confirm PV isolation using standard practice. 3. Adverse events Reporting.

PRIMARY ENDPOINTS
	
 1. The accuracy, sensitivity, specificity and positive and negative predictive values of the KODEX-EPD PV occlusion feature as compared to conventional venographic method of fluoroscopy with contrast dye that will be used to guide the procedure. 2. The success of the freeze when freeze is initiated based on the assessment of the KODEX-EPD PV occlusion feature as compared to the success of the freeze when freeze is

	initiated based on the assessment with fluoroscopy and contrast dye.
SECONDARY/ EXPLORATORY ENDPOINTS	
Procedure data collection:
 
• KODEX-EPD data collection• Fluoroscopy system data collection• Fluoroscopy time• Fluoroscopy dose• Number of contrast dye injections• Contrast dye volume• Information on durability of the PV isolation.• Time to isolation (TTI)/Success of Isolation• Number of ablations per vein• Procedure time (skin to skin)
SPONSOR	EPD Solutions is the sole study sponsor. This study will be conducted according to US 21 CFR 11, 50, 54, 56, 812, ISO 14155: 2020, the ICH Guidelines for GCP, the Declaration of Helsinki (2013) and all other applicable local and national regulations. The study will be registered on www.clinicaltrials.gov .

Acronyms and Definitions

AE	Adverse Event
CRF	Case Report Form
EMR	electronic medical record
EP	electrophysiology
ESI	Event of Special Interest
HU	Healthcare Utilization
ICF	Informed Consent Form
SAE	Serious Adverse Event
USADE	Unanticipated Serious Adverse Device Effect

1. BACKGROUND AND RATIONALE

1.1. Overview of Disease

1.1.1. *Arrhythmias*

Cardiac arrhythmias are common and produce considerable morbidity and mortality and are challenging to treatⁱ. Symptoms such as dizziness, palpitations, and syncope are frequent complaints encountered by family physicians, internists, and cardiologists. In contrast to these ubiquitous complaints, which are generally benign, sudden cardiac death remains an important public health concern. Statistics from the Centers for Disease Control and Prevention (CDC) have estimated sudden cardiac death rates at more than 600,000 per year. Up to 50% of patients have sudden death as the first manifestation of cardiac diseaseⁱⁱ.

Arrhythmias are one of the most complexes, insufficiently studied, and therefore one of the most urgent problems of modern cardiology. With a wide introduction in the practice of ECG monitoring by Holter as well as the use of individual recorders of electrocardiogram data appeared indicating a much higher frequency of cardiac arrhythmiasⁱⁱⁱ.

Enormous advances in arrhythmia management have occurred over the 60 years, but important challenges remain. Challenges in diagnosis, detection, and risk-stratification include difficulties in separating benign from high-risk syncope and pinpointing the underlying causes and inadequate identification of sudden-death risk.

As of 2012, approximately 4.3 million Americans experienced some form of cardiac arrhythmia. Annually, 5,750,440 individuals experienced cardiac arrhythmia in the US. Total direct annual healthcare cost of cardiac arrhythmia summed up to \$US67.4 billion. Cardiac arrhythmias represent a substantial economic burden in the US, especially for the older adult population^{iv}.

1.1.2. *Current Treatment Options*

Pharmacologic therapy for arrhythmia is widely used however catheter ablation offers encouraging results in the treatment of most cardiac arrhythmias and is considered as a first line therapy by international guidelines.^{v, vi} Furthermore in the treatment of Atrial Fibrillation (AF) catheter ablation is considered superior regarding freedom of arrhythmia recurrence compared to anti-arrhythmic drug therapy.^{vii, viii, ix}

Current catheter-based therapy utilizes cardiac 3D mapping and navigation systems that were introduced more than 20 years ago and allow location of the ablation device within a reconstruction of the heart anatomy^{x, xi, xii, xiii}. However, technical limitations specific to each available 3D mapping system, such as variability in catheter tip location sensing, alternating location reliability throughout the procedure, and the use of costly specialized catheters and additional hardware (e.g. magnets placed under the operating table, pose limitations of these systems. Furthermore, all available systems provide only an estimate of each individual anatomy, as they do not provide high-quality, real-time

visualization of anatomical structures, but merely a low-resolution reconstruction. In order to obtain more information and a precisely detailed anatomy, time consuming and often costly additional imaging such as fluoroscopy, angiography, echocardiography and even pre-procedural computer tomography (CT) and magnetic resonance imaging (MRI) is required in many cases^{xiv}.

In conclusion the current procedures are relatively long, considered highly complex and require substantial expertise. In addition specialized catheters and additional hardware is required. The Sponsor has identified these challenges and has developed the KODEX - EPD system to address them successfully.

1.1.3. *Cryoballoon Ablation Therapy and Technology*

Pulmonary vein isolation (PVI), by catheter ablation, represents the current treatment for drug-resistant AF^{xv}. Due to its ease of use, fast procedures and durability of lesions in a high percentage of PVs leading to excellent clinical outcome, Cryoballoon Ablation is a recognized ablation method in patients with atrial fibrillation^{xvi}. However, cryoballoon ablation requires extensive fluoroscopic guidance to position the balloon catheter at the pulmonary veins often leading to prolonged radiation exposure and possible contract induced kidney injury.

1.2. KODEX-EPD System

1.2.1. *Description of the KODEX-EPD System*

The KODEX - EPD system is an open platform that uses any validated EP catheter to create real-time 3D images of the human heart. The KODEX-EPD system takes advantage of the unique dielectric properties of biological tissue by inducing anisotropic electrical fields within the patients' body and measuring the resultant subtle electrical field differences on the catheter electrodes as they move in the hearts' chambers. The anisotropic fields are induced by one or multiple sources such as external sensors on the body surface and the diagnostic and/or an ablation catheter. The system receives and analyzes the electrical field transmission and reflection from all catheter electrodes as they are manipulated in the cardiac chambers. Structures such as the endocardial atrial surface, cardiac veins, and heart valves cause marked gradients in the electrical field. This "bending of the electrical field" is sensed by the system and used to calculate the geometric characteristics of the three-dimensional (3D) image. With this technique, the KODEX-EPD System collects anatomic information, without immediate physical surface contact, a few millimeters ahead of the catheter electrodes, resulting in a certain degree of "far-field imaging". The catheter serves as an internal distance ruler for scaling of the geometry by comparing the known inter electrode spacing versus the voltage difference between the 2 electrodes. The system records a specific set of electrical field descriptors for each specific position of the catheter within the cardiac anatomy and can thereby determine relative positions and distances between locations within the chamber. At each location, the electrical field descriptors that the KODEX-EPD System acquires are used to reconstruct the chamber geometry.^{xvii}

1.2.1.1. Study device

The KODEX-EPD system is manufactured by;

Philips Medical Systems Nederland B.V.

[name]

[name]

The Netherlands

The study device hardware consists of a;

- Processing Unit (version 1.2)
- Workstation
- Body Surface pin box
- Diagnostic Catheter pin box (2x)
- Recording system pin box (2x)
- Foot Pedal

Figure 1: System Overview

The most recent commercialized version of the software will be used for the purpose of this study. Currently this is software version 1.4.8

The KODEX-EPD system is designed to be used with validated commercially available diagnostic and therapeutic catheters. The KODEX-EPD System is supported with dedicated KODEX-EPD sensors and catheters activation keys for RF and Cryo ablation interventions.

[figure not shown]
[figure not shown]

Figure 2: Procedural Disposables

The KODEX - EPD system interfaces with the following commercially available components and devices:

1. **Display:** shows in real-time, and throughout the procedure, the cardiac chamber's geometry and all indwelling catheters.

2. **RF generator:** commercially available RF generators can be connected to the KODEX - EPD system PU, which is then connected to the ablation catheter. The following commercially available RF generators have been tested with the KODEX - EPD system PU:
 - KODEX - EPD RF Ablation System
 - Stockert 70 (Biosense Webster) RF Generator
 - SmartAblate (Biosense Webster) RF Generator
 - Maestro 4000 (Boston Scientific) RF Generator
3. **Standard EP diagnostic and ablation catheters:** for a full list of commercially available compatible catheters, refer to KODEX - EPD system List of Compatible Catheters.
4. **Recording system (includes pacer connection):** commercially available recording systems, such as Prucka CardioLab EP Recording System (General Electric) or LABSYSTEM PRO (Boston Scientific).

1.2.1.2.KODEX-EPD system updates.

The Instructions for use (IFU) will be provided containing the information on the most current software and hardware versions that will be used. Please note that the CIP will not be updated if the hardware/software version is updated unless the update results in;

- an updated clinical workflow described in this CIP;
- an updated benefit-risk analysis;
- an update to the study design;
- an update to the data to be collected;
- any other update that would affect the execution of this clinical investigation.

1.2.2. Intended Use

The KODEX-EPD system has received FDA approval and CE mark for creating real-time 3D images of the human heart using validated commercially available diagnostic and therapeutic catheters. For the purpose of this study we will be using the KODEX-EPD system in its intended use as described in the User Manual

1.2.2.1.Training and Experience

Trained sponsor personnel will be responsible for the set-up of the KODEX-EPD system and will operate the system during the procedure. Physicians completing the EP procedures will have received training on the KODEX-EPD system prior to including the first subject in the study. This training is outside the scope of the study.

1.2.3. Limitations for use

There are no special clinical situations that could potentially affect or limit the system performance and accuracy.

1.2.4. Exposure to Study Device

The KODEX-EPD System is used to assist the physician during cardiac ablation procedures in patients with a cardiac arrhythmia. The patient will be connected to the KODEX-EPD system via the KODEX-

EPD sensors shown in Figure 2. The duration of exposure to the Study device for both the operator and patient will be the length of the cardiac ablation procedure.

1.3. Study design justification

1.3.1. *(Pre)Clinical Studies with the KODEX-EPD System*

The system's measurement and localization capabilities have been validated and the location accuracy and distance score measurements demonstrated that the system is highly accurate, whereas the DURABLE-I clinical study demonstrated safety and efficacy of the KODEX-EPD system. Another study demonstrated that the 3D image quality generated by the KODEX-EPD system is noninferior to CARTO 3 (Biosense Webster) and accurately detects catheter location^{xviii}. Clinical data to date has not demonstrated any adverse device effects.

1.3.1.1. Cryo Occlusion feature:

The performance of the Cryo Occlusion feature was validated by means of retrospective analysis of a database of KODEX files from routine cases for which the occlusion status on venography was available as ground truth. For each occlusion event from the database the occlusion status on KODEX was determined with the final version of the KODEX occlusion algorithm and compared against the corresponding occlusion status on venography as ground truth. The accuracy of the Cryo Occlusion feature for the baseline workflow was 92.1%, and for the injection workflow 90.4%, both of which exceed the pre-defined acceptance criteria of $\geq 90\%$. The clinical acceptability of the workflow of the Cryo Occlusion feature was evaluated by replay of a subset of the KODEX files (n=10) from the database with a final version of KODEX software. During replay of these cases, five clinical specialists filled in a questionnaire in which they each answered questions related to four user requirements of the Cryo Occlusion workflow and provided a score using a 5-point Likert scale. The average scores were 4.0, 4.4, 3.6, and 3.6, and thereby the test was passed because the pre-defined acceptance criteria was ≥ 3 .

1.3.2. *Relevant Literature on the KODEX-EPD System Cryoballoon Occlusion feature*

Several manuscripts on the occlusion feature have been published to date, ^{xix,xx,xxi,xxii}, reporting that the KODEX-EPD Occlusion feature is safe, feasible, and effective in assessing the degree of PV occlusion during AF cryoablation.

1.3.3. *Study Justification*

Current clinical studies on the KODEX-EPD occlusion feature have reported on the safe and effective use of the system in standard practice. However, the performance of the KODEX-EPD occlusion feature has not been evaluated using a standardized workflow in a blinded setting in a homogenous patient group. Furthermore, in an effort to minimize therapy, a direct comparison between the success of the freeze when initiating therapy based on the occlusion feature vs the assessment of occlusion by fluoroscopy has not been evaluated. The study design indicates a post-market interventional clinical

investigation to evaluate the endpoints of the study. No follow-up is foreseen ensuring a minimal burden to the subjects participating in the study.

2. EXPERIMENTAL PLAN

2.1. Study Objectives

The study objective is to evaluate the performance of the KODEX-EPD PV occlusion feature as compared to conventional venographic method of fluoroscopy with contrast dye in cryoballoon procedures that is used to guide the procedure. Performance will be calculated in terms of accuracy, sensitivity, specificity and positive and negative predictive values. In the blinded arm of this 2-armed study, the operator will be blinded for the PV occlusion data on the KODEX-EPD system, and this data will not be used for clinical guidance. In the KODEX guided arm the operator will use the KODEX-EPD system occlusion data to guide the procedure.

2.2. Study Design

2.2.1. Study Schematic

[figure not shown]

Figure 3; Study Schematic

The Cryoballoon procedure consists of the isolation and ablation of the pulmonary veins (PVs). The number of PVs and occlusion tests per PV depends on several factors including patient anatomy. Therefore, data from the KODEX-EPD PV Occlusion feature will be evaluated as a separate set of data for each occlusion test and for each pulmonary vein. Data from a PVI where the diameter of the (common) PV ostium > 28mm, or when the threshold for Distance to Shadow (DTS), Distance to Mesh (DTM) or Distance to Ostium (DTO) is exceeded, or when the Achieve catheter is moving during the

injection, there is a double injection or an incorrect timing of the injection, will not be included in the primary endpoint analysis.

2.2.2. Primary Endpoints

1. The accuracy, sensitivity, specificity and positive and negative predictive values of the KODEX-EPD PV occlusion feature as compared to conventional angiographic method of fluoroscopy with contrast dye that will be used to guide the procedure.
2. The success of the freeze when freeze is initiated based on the assessment of the KODEX-EPD PV occlusion feature as compared to the success of the freeze when freeze is initiated based on the assessment with fluoroscopy and contrast dye.

2.2.3. Secondary and Exploratory Endpoints

Procedure data collection:

- KODEX-EPD data collection
- Fluoroscopy system data collection
- Fluoroscopy time
- Fluoroscopy dose
- Number of contrast dye injections
- Contrast dye volume
- Time to isolation (TTI)/Success of Isolation
- Number of ablations per vein
- Procedure time (skin to skin)

2.2.4. Study Duration

The study enrolment is expected to take 1.5 years. The study has no F/Up therefore the total duration is expected to be 1.5 years.

2.3. Study Centers

In total Two (2) centers; Johns Hopkins University in Baltimore, USA and UZ Brussel in Brussel, Belgium will participate in the study

2.4. Number of patients

A maximum of 20 patients per center will be included in the blinded to KODEX arm of the study. An additional 25 patients will be included at UZ Brussel in the KODEX guided arm of the study.

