5.4.2.1. Primary Endpoint Analyses

Results will be summarized by occlusion test, by PV and by patient.

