5.5. Data justification

Systemic error/bias will be minimized by having operators select subjects from their general patient population. Before enrolling subjects, sites/operators will be trained on the study protocol to ensure consistency across sites/operators. Subjects will be equally distributed over the 2 sites in the blinded arm of the study.

5.5.1. *Missing Data*

No imputations for missing data will be made. This is an acute study with no F/Up foreseen.

5.5.2. *Deviations*

Any changes to the planned statistical analyses made will be documented in a separate Statistical Analysis Plan. Changes from the planned statistical methods will be documented in the clinical study report along with a reason for the deviation. Post-hoc analyses may be conducted according to the existing data collected, if necessary

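### Endpoint 2 sets a single-site guided arm against a two-site blinded arm with no same-site contrast, so the pooled difference carries about half of any site gap

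*Combined protocol and SAP*

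**What the plan says.** Sections 2.2.2 and 5.1.1 word the second primary endpoint as a comparison: "The success of the freeze when freeze is initiated based on the assessment of the KODEX-EPD PV occlusion feature as compared to the success" of freezes started on fluoroscopy with contrast.

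The arms draw on different sites:

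- **Guided arm (Section 2.4):** "An additional 25 patients will be included at UZ Brussel in the KODEX guided arm of the study".
- **Blinded arm (Sections 2.4 and 5.5):** at most 20 patients at each of two centers, and "Subjects will be equally distributed over the 2 sites in the blinded arm of the study".

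The synopsis describes the design as "Prospective, multi-center, non-randomized, open label, double arm study". The readable text does not say how a UZ Brussel patient is placed in one arm or the other (Figure 3 is not reproduced in the text available).

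Section 5.2 defines the primary analysis set as all successful occlusion tests, without restriction by site. For the primary endpoints, Section 5.4.2.1 says: "Results will be summarized by occlusion test, by PV and by patient". Section 5 contains no site summary, site adjustment or same-site comparator. On consistency, Section 5.5 says that "sites/operators will be trained on the study protocol to ensure consistency across sites/operators", and it has operators choose subjects from their general patient population.

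**The concern.** Johns Hopkins contributes nothing to the guided arm and about half of the blinded arm. Any difference between the sites in operators, patients or technique is thus partly mixed with the difference between guidance methods. Section 5.5 does not deal with this. Its equal split balances sites within the blinded arm, which is exactly what makes the two arms differ in site mix. Drawing patients from each operator's own practice does not make the two practices alike.

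There is room for sites to differ despite the common workflow. Section 2.6.2.1 allows an auto-injector or a manual syringe, and in the blinded arm occlusion is judged on fluoroscopy by the physician (Section 2.6.7.3). Training may narrow a gap but cannot be assumed to remove it.

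At stake is the direct comparison of freeze success that Section 1.3.3 gives as part of the reason for the study. A site gap could appear as a KODEX benefit, or could hide one.

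**Working it through.** **The plan's own figure.** Section 5.3 sizes endpoint 2 at 87, from an expected 80% and a lower limit of about 70%. The exact (Clopper-Pearson) lower limit with 2.5% in the lower tail first reaches 70% at n = 87 (limit 0.7005), so the figure reproduces. It concerns one proportion in the guided arm; the comparison was not sized.

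**Share of the site gap.** Let d be freeze success at UZ Brussel minus that at Johns Hopkins under the same guidance, and s the Johns Hopkins share of blinded units. With no device effect:

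- guided arm = U (UZ Brussel success)
- blinded arm = (1 − s)U + s(U − d) = U − s·d
- pooled difference = s·d

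By patients, s = 20/40 = 0.50 at the Section 2.4 maximum, or 15/30 = 0.50 at the Section 5.3 size. By freezes or veins s can move, because "The number of PVs and occlusion tests per PV depends on several factors including patient anatomy". A share of 0.4 or 0.6 corresponds to Johns Hopkins contributing 0.67 or 1.5 times as many units per patient as UZ Brussel.

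Shift in the pooled difference, in points, for assumed gaps:

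| s | d = 5 | d = 10 | d = 15 |
|---|---|---|---|
| 0.4 | 2 | 4 | 6 |
| 0.5 | 2.5 | 5 | 7.5 |
| 0.6 | 3 | 6 | 9 |

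**Precision cost of the same-site contrast.** Half-width = 1.96 × √{DE × (p1q1/n1 + p2q2/n2)}, with q = 1 − p and DE = 1 + (v − 1) × ICC, where v is evaluable veins per patient.

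- v = 4 is implied by Section 5.3 (120/30 = 4.0; 87/22 = 3.95), though that section does not name the unit. v = 3 allows for the exclusions in Section 2.2.1.
- p1 = p2 = 0.80. Section 5.3 gives 80% for the guided arm only.
- ICC 0, 0.1 and 0.2 are assumed.
- 25 guided patients; 40 blinded patients (maximum) or 30 (Section 5.3), half of them at UZ Brussel.

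Example, v = 4, 40 blinded, DE = 1: pooled 1.96 × √{0.16 × (1/100 + 1/160)} = 9.99 points; same-site 1.96 × √{0.16 × (1/100 + 1/80)} = 11.76 points.

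| v | Blinded patients | DE | Pooled | Same-site | Extra |
|---|---|---|---|---|---|
| 4 | 40 | 1.0 | 9.99 | 11.76 | 1.8 |
| 4 | 40 | 1.6 | 12.64 | 14.88 | 2.2 |
| 4 | 30 | 1.0 | 10.62 | 12.80 | 2.2 |
| 4 | 30 | 1.6 | 13.43 | 16.19 | 2.8 |
| 3 | 40 | 1.0 | 11.54 | 13.58 | 2.0 |
| 3 | 40 | 1.4 | 13.65 | 16.07 | 2.4 |
| 3 | 30 | 1.0 | 12.26 | 14.78 | 2.5 |
| 3 | 30 | 1.4 | 14.50 | 17.49 | 3.0 |

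With v = 4, comparator success of 70% gives 2.16 to 3.36 extra points, and 90% gives 1.12 to 1.79.

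**Which contrast has the smaller error.** At s = 0.5 the pooled mean squared error is Var(pooled) + (d/2)², and the same-site one is Var(same-site). They are equal at d = 2√{Var(same-site) − Var(pooled)}. For v = 4, 40 blinded, DE = 1, this is 2√(0.0036 − 0.0026) = 6.3 points; for 30 blinded, DE = 1.6, it is 9.2. For v = 3 the range is 7.3 to 10.0. Pooling has the smaller error below the break-even gap, and the same-site contrast above it.

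**The case against.** The strongest reply is that no harm is shown. The documents give neither the size nor the direction of a site gap, and nothing ties the injection options or visual reading to one site. Section 5.4.1 plans no inference, endpoint 2 is sized on one proportion, and for modest gaps pooling has the smaller error. Section 5.5.2 permits post-hoc analyses, so site could be tabulated later. On this view the point is a minor reporting clarification.

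Part of this stands. The gap is unknown, the shifts are illustrations, and neither contrast can be ranked first. The precision figures rest on an inferred unit: Section 5.3 does not say what 87 and 120 count, Section 5.2 works in occlusion tests, and the endpoint concerns freezes. The readable text does not define freeze success. Nor does it state the basis of a guided-arm freeze after three KODEX attempts without occlusion. Those are separate questions, and a same-site contrast does not settle them.

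The rest does not answer the point. A descriptive difference can be biased too. The unrestricted analysis set in Section 5.2 makes pooling the natural reading. The independent image review in Section 2.6.7.3 cannot change which freezes were started. A comparator chosen after the results are seen is weaker than one fixed beforehand.

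**Conclusion.** The concern holds and should be fixed. Taken as written, the plan leads to a pooled endpoint 2 difference that carries about half of any site gap in freeze success. The share is exactly half only if both sites supply equal numbers of blinded freezes or veins. Confidence in this structural point is high, since it follows from the plan's own enrolment figures.

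The size of the bias is unknown: 2.5 to 7.5 points for assumed gaps of 5 to 15 points at equal shares, and 2 to 9 points as the Johns Hopkins share runs from 40% to 60%. The effect is confined to the endpoint 2 comparison. Endpoint 1 and the guided-arm proportion taken alone are not affected by this imbalance. The break-even results support reporting both contrasts.

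**What to change.** Before any interim or final summary, amend Section 5.4.2.1, or use the route in Section 5.5.2 ("Any changes to the planned statistical analyses made will be documented in a separate Statistical Analysis Plan"), to state that endpoint 2 will be reported as:

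1. the same-site contrast, guided versus blinded patients at UZ Brussel;
2. the pooled contrast, guided versus all blinded patients;
3. the Johns Hopkins blinded results shown separately.

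Give each contrast as a descriptive difference in proportions with a patient-clustered 95% interval and no test. Any statement about KODEX versus fluoroscopy should cite the two contrasts side by side and say that both are non-randomized. Record how and when each UZ Brussel patient was placed in an arm.

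The cost is SAP text, or a CIP amendment with IRB/EC authorization under the amendments section, plus one recorded item. No extra patients or outcome data are needed: up to 20 blinded UZ Brussel patients are already planned. At 80% success in both arms, the same-site half-width is wider by about 1.8 to 2.8 points with four evaluable veins per patient, or 2.0 to 3.0 with three. The two estimates may differ and need explaining. Selection between arms, and any period difference, within UZ Brussel would remain.
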